³ Patients who withdraw/discontinue from the study early should have all Week 12 assessments performed.

⁴ FSH test for post-menopausal women only.

⁵ Pregnancy test for females of childbearing potential only.

⁶ Blood and urine samples should be drawn/collected prior to dose of Study Medication when dose is administered in the clinic.

⁷ CTP-692 blood samples should be taken pre-dose at Weeks 2, 4, 6, 8, and 10 when dose is administered in the clinic, and post-dose at Week 12.

⁸ Patients must sign the optional genetic blood sample genetic research consent form.

⁹ Due to the COVID-19 pandemic and the possibility for site closures and/or travel restrictions, clinical laboratory blood draws may be performed by a Home Health Care service provider or by a local laboratory; other safety and efficacy assessments may be performed remotely via phone/audio or video conferencing platforms (with the exception of Facebook).

¹⁰ When study assessments are not conducted in the clinic due to the COVID-19 pandemic, the Study Medication may be sent directly to the patient.

¹¹ Due to the COVID-19 pandemic and the possibility for site closures and/or travel restrictions, if Week 6 is a remote visit, ECG assessment may be performed at Week 8 or Week 10.

¹² Due to the COVID-19 pandemic, the Safety Follow-up may be conducted remotely per Investigator discretion.

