- Standard 12-lead ECG (Weeks 6 and 12 only; if Week 6 visit is a remote visit, ECG assessment may be performed at Week 8 or 10)
- Urine pregnancy tests for women of childbearing potential
- Alcohol breath test
 - o *Patient may be discontinued if they test positive at any two visits during the treatment period*
- Serum chemistry, hematology, and coagulation parameter evaluations (Weeks 6 and 12 only)
- Serum renal parameters and urinalysis
- Blood sample for assessment of CTP-692 levels (pre-dose if dose of Study Medication is administered in the clinic at Weeks 2, 4, 6, 8, and 10)
 - o *If possible, time of last dose taken should also be recorded*
- Dispensation of Study Medication to take home
 - *A 2-week supply of the Study Medication will be provided at each visit except Week 12*
 - *When study assessments are not conducted in the clinic due to the COVID-19 pandemic, the Study Medication may be sent directly to the patient*
- PANSS (Weeks 2, 4, 8, 10, and 12)
- CGI-S (Weeks 2, 4, 6, 8, 10, and 12)
- C-SSRS (Since Last Visit version)
- PSP (Weeks 6 and Week 12 only)
- SQLS (Week 12 only)
- SAS, AIMS and BARS (Weeks 6 and Week 12 only)
- Blood sample for assessment of CTP-692 levels (post-dose; Week 12 only)
 - *Blood sample should be taken at the end of the visit*
 - *Time of CTP-692 dose and blood draw should be recorded*
- Administration of dose of Study Medication in the clinic with food *at the Week 12 visit*
 - Post Dose blood sample for assessment of CTP-692 levels (Week 12 only)
 - o *Blood sample should be taken at the end of the visit*
 - o *Time of CTP-692 dose and blood draw should be recorded*

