13.2.2 Safety

Safety of CTP-692 will be assessed by evaluating adverse events, vital signs, concomitant medications, clinical laboratory parameters including blood urea nitrogen (BUN) and creatinine, urinalysis, ECG results, as well as physical examinations. Extrapyramidal symptoms (EPSs) will be evaluated using SAS, AIMS, and the BARS. Assessment of suicidality will be performed at every visit using the C-SSRS.

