APPENDIX G: SIMPSON-ANGUS SCALE (SAS)

Patient Name: _____ Date: _____

SIMPSON-ANGUS EXTRAPYRAMIDAL SIDE EFFECTS SCALE

The exam should be conducted in a room where the subject can walk a sufficient distance to allow him/her to get into a natural rhythm (e.g. 15 paces). Each side of the body should be examined. If one side shows more pronounced pathology than the other, this score should be noted and this taken. Cogwheel rigidity may be palpated when the examination is carried out for items 3, 4, 5, and 6. It is not rated separately and is merely another way to detect rigidity. It would indicate that a minimum score of 1 would be mandatory.

1. **Gait:** The patient is examined as he walks into the examining room, his gait, the swing of his arms, his general posture, all form the basis for an overall score for this item. This is rated as follows:
 - 0 Normal
 - 1 Diminution in swing while the patient is walking
 - 2 Marked diminution in swing with obvious rigidity in the arm
 - 3 Stiff gait with arms held rigidly before the abdomen
 - 4 Stooped shuffling gait with propulsion and retropulsion
2. **Arm Dropping:** The patient and the examiner both raise their arms to shoulder height and let them fall to their sides. In a normal subject, a stout slap is heard as the arms hit the sides. In the patient with extreme Parkinson's syndrome, the arms fall very slowly:
 - 0 Normal, free fall with loud slap and rebound
 - 1 Fall slowed slightly with less audible contact and little rebound
 - 2 Fall slowed, no rebound
 - 3 Marked slowing, no slap at all
 - 4 Arms fall as though against resistance; as though through glue
3. **Shoulder Shaking:** The subject's arms are bent at a right angle at the elbow and are taken one at a time by the examiner who grasps one hand and also clasps the other around the patient's elbow. The subject's upper arm is pushed to and fro and the humerus is externally rotated. The degree of resistance from normal to extreme rigidity is scored as follows:
 - 0 Normal
 - 1 Slight stiffness and resistance
 - 2 Moderate stiffness and resistance
 - 3 Marked rigidity with difficulty in passive movement
 - 4 Extreme stiffness and rigidity with almost a frozen shoulder
4. **Elbow Rigidity:** The elbow joints are separately bent at right angles and passively extended and flexed, with the subject's biceps observed and simultaneously palpated. The resistance to this procedure is rated. (The presence of cogwheel rigidity is noted separately.)
 - 0 Normal

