 - 1 Slight stiffness and resistance
 - 2 Moderate stiffness and resistance
 - 3 Marked rigidity with difficulty in passive movement
 - 4 Extreme stiffness and rigidity with almost a frozen elbow
5. **Wrist Rigidity or Fixation of Position:** The wrist is held in one hand and the fingers held by the examiner's other hand, with the wrist moved to extension, flexion and ulnar and radial deviation:
 - 0 Normal
 - 1 Slight stiffness and resistance
 - 2 Moderate stiffness and resistance
 - 3 Marked rigidity with difficulty in passive movement
 - 4 Extreme stiffness and rigidity with almost frozen wrist
6. **Leg Pendulousness:** The patient sits on a table with his legs hanging down and swinging free. The ankle is grasped by the examiner and raised until the knee is partially extended. It is then allowed to fall. The resistance to falling and the lack of swinging form the basis for the score on this item:
 - 0 The legs swing freely
 - 1 Slight diminution in the swing of the legs
 - 2 Moderate resistance to swing
 - 3 Marked resistance and damping of swing
 - 4 Complete absence of swing
7. **Head Dropping:** The patient lies on a well-padded examining table and his head is raised by the examiner's hand. The hand is then withdrawn and the head allowed to drop. In the normal subject the head will fall upon the table. The movement is delayed in extrapyramidal system disorder, and in extreme parkinsonism it is absent. The neck muscles are rigid and the head does not reach the examining table. Scoring is as follows:
 - 0 The head falls completely with a good thump as it hits the table
 - 1 Slight slowing in fall, mainly noted by lack of slap as head meets the table
 - 2 Moderate slowing in the fall quite noticeable to the eye
 - 3 Head falls stiffly and slowly
 - 4 Head does not reach the examining table
8. **Glabella Tap:** Subject is told to open eyes wide and not to blink. The glabella region is tapped at a steady, rapid speed. The number of times patient blinks in succession is noted:
 - 0 0-5 blinks
 - 1 6-10 blinks
 - 2 11-15 blinks
 - 3 16-20 blinks
 - 4 21 and more blinks
9. **Tremor:** Patient is observed walking into examining room and is then reexamined for this item:
 - 0 Normal
 - 1 Mild finger tremor, obvious to sight and touch
 - 2 Tremor of hand or arm occurring spasmodically
 - 3 Persistent tremor of one or more limbs
 - 4 Whole body tremor

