### **3.6 COVID-19 Considerations**

Due to the COVID-19 pandemic, some assessments may be conducted remotely. These will be treated the same as on-site assessments and will be aggregated with data from the on-site assessments for analysis.

In case of two consecutive missed safety assessments due to the COVID-19 pandemic, continued patient participation in the study must be discussed by the Investigator and the Medical Monitor.

A patient who prematurely discontinues Study Medication/study participation should have all Week 12 assessments performed as an Early Termination Visit, and if possible, return for the Safety Follow-up Visit. The Safety Follow-Up Visit may be waived by the Sponsor in instances where patients have discontinued dosing prior to the Early Termination Visit on a case-by-case basis.

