#### **5.5.7 *Extrapyramidal Symptoms***

Scores on the SAS, AIMS, and BARS will be summarized for each corresponding visit. Individual patient scores will be listed.

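### Remote visits may include the Simpson-Angus scale, which cannot be completed without physical contact; the plan pools remote with clinic ratings and gives a remote Week 6 no deferral like the ECG's

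*Protocol*

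**What the plan says.** **Permission.** For the Treatment Period, Protocol Table 6 footnote 9 says that "other safety and efficacy assessments may be performed remotely via phone/audio or video conferencing platforms (with the exception of Facebook"). Protocol 7.1, 8.2.2 (Weeks 2 to 12) and 11 repeat this, as do SAP Table 1 footnote 9 and SAP 3.6.2. Blood draws have their own arrangement (home health service or local laboratory).

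**Scales and schedule.** Protocol 13.2.2 makes the three scales part of the safety evaluation: "Extrapyramidal symptoms (EPSs) will be evaluated using SAS, AIMS, and the BARS". After Day 1, Protocol 8.2.2 schedules "SAS, AIMS and BARS (Weeks 6 and Week 12 only"). Patients who leave early have the Week 12 set at an Early Termination visit.

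**Exceptions already written.** The PANSS may not be done remotely during Screening (Protocol 8.2.1). The follow-up brief physical examination is done only if that visit is in the clinic (8.2.3). For the ECG, Table 6 footnote 11 says "if Week 6 is a remote visit, ECG assessment may be performed at Week 8 or Week 10". The extrapyramidal (EPS) scales have no such provision.

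**Missed assessments.** Protocol 7.1, 8.2.2 and 11 accept that some assessments may prove impossible and have them recorded as missed because of COVID-19. Section 11 gives safety assessments priority.

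**Analysis.** SAP 3.6 says of remote assessments: "These will be treated the same as on-site assessments and will be aggregated with data from the on-site assessments for analysis". SAP 5.5.7 says: "Scores on the SAS, AIMS, and BARS will be summarized for each corresponding visit". It neither splits by mode of visit nor gives a rule for an incomplete SAS. SAP 5.1.4 generally leaves missing data unimputed and provides a listing of missing or remote visits due to COVID-19.

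**The concern.** The permission and the pooling rule together admit a rating that cannot be carried out as the protocol defines it. Several SAS items measure resistance felt by the examiner, and a camera or telephone cannot supply that. With only two post-baseline ratings per patient, a remote Week 6 visit puts half of that patient's planned post-baseline SAS data at risk, even when the patient is back in the clinic two weeks later. The protocol recognised this for the ECG and let it move, but gave the EPS scales no such route.

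At stake is the EPS safety summary in a population all of whom take an antipsychotic. Day 1 is rated in the clinic, so a partial remote rating entered as a full one would not be comparable with its own baseline.

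**Working it through.** The plan gives no figure for EPS, so there is none to reproduce. The check compares the rating instructions with the remote-visit and pooling rules.

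**1. Are the scales covered?** They are named safety assessments (Protocol 13.2.2), are due at Weeks 6 and 12 (8.2.2) and fall inside the Week 2 to 12 block where remote assessment is allowed. No section exempts them.

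**2. Which SAS items need contact?** From the Appendix G instructions:

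- Item 3, shoulder: the arms "are taken one at a time by the examiner who grasps one hand", with the other hand around the elbow.
- Item 4, elbow: joint moved passively, biceps palpated.
- Item 5, wrist: "The wrist is held in one hand and the fingers held by the examiner's other hand".
- Item 6, leg: examiner lifts the ankle and releases it.
- Item 7, head: examiner raises the head and withdraws the hand.
- Item 8, glabella: examiner taps.
- Items 1 (gait), 2 (arm dropping), 9 (tremor) and 10 (salivation): observation.

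Contact items: 6 of 10. Video leaves 4; audio alone leaves essentially none that can be rated as written.

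Protocol 11.7.1 and SAP 4.6.1 describe a different SAS. They list head rotation and akathisia in place of leg pendulousness and head dropping. Taking shoulder, elbow, wrist, head rotation and glabella as contact items gives about 5 of 10. It is only about five because neither section says how head rotation is examined.

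**3. Can a total be formed?** Both sections define the total as the sum over all ten items. With contact items blank, there is no total. With them entered as normal, the highest total reachable by video is:

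- Appendix G (items 0 to 4): 4 × 4 = 16 of 40, so 24/40 = 60% of the range is out of reach.
- Protocol 11.7.1 and SAP 4.6.1 (items 1 to 5): 5 × 5 + 5 × 1 = 30 of 50.

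These are ceilings. They show that the total is not valid; they do not give an expected bias.

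**4. AIMS and BARS.** AIMS movements and the BARS objective item must be seen, so video can serve. With audio alone, what remains is patient report: AIMS item 10 and BARS items 2 and 3.

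**5. What does a remote Week 6 produce?** If SAS is recorded as missed, one of two post-baseline ratings is lost. If unexamined items are scored as normal, the total is biased low against Day 1, and SAP 3.6 pools it as it stands. The ECG route would recover the rating at Week 8 or 10, that is 56 − 42 = 14 or 70 − 42 = 28 days after the Week 6 target day in SAP Table 2.

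**6. Size.** Suppose every unexamined item were scored as normal on the 0 to 4 form. The pooled mean would then be understated by s × f, where s is the share of the true score carried by contact items and f the fraction of visits that are remote. The documents give neither. Assuming s from 0.4 to 0.8 and f from 0.1 to 0.5:

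- 0.4 × 0.1 = 4%
- 0.6 × 0.25 = 15%
- 0.8 × 0.5 = 40%

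The range restates its assumptions and is not an estimate.

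**The case against.** A reader might infer that remote SAS scores will be falsely low, will look like improvement and will pull every arm toward zero. The documents do not support that. No section tells raters to enter 0 for an item they did not examine. In Appendix G a 0 generally describes something found on examination. The missed-assessment wording and SAP 5.1.4 both point to a missing value. The revised eCRFs (Protocol 15.4) are not available to show what they accept. Low bias is therefore a conditional outcome, and a missing value is the more natural one.

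Nor is it right that all three scales fail at every remote visit: AIMS and BARS are largely ratable by video.

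It can also be said that footnote 9 is permissive and limited by feasibility; read literally it would equally allow weight or vital signs by telephone. That is fair, but the limit is left to each site, and the pooling rule in SAP 3.6 has no such limit. Elsewhere the protocol does write the restriction down, as for the ECG and the follow-up physical examination.

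Other safeguards exist. Adverse events are collected throughout, phone check-ins fall between visits, two consecutive missed safety assessments prompt a discussion with the Medical Monitor, and remote visits are listed. The Phase 1 adverse event tables in Protocol 4.2 show no extrapyramidal event, although those were healthy volunteers dosed once or for seven days. These points lower the stakes. They neither recover a Week 6 rating nor keep an invalid total out of a table.

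The lack of change from Day 1 in SAP 5.5.7 is mainly a presentation matter: Day 1 is itself a scheduled EPS visit, and the table shells are a separate document.

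**Conclusion.** The point holds in a limited form. The plan permits a remote SAS that cannot be completed as defined, pools whatever is recorded, and gives no route to recover a remote Week 6 rating at the next clinic visits. For AIMS and BARS the problem is confined to audio-only visits. The count of contact items is six of ten on Appendix G and about five on the list in Protocol 11.7.1 and SAP 4.6.1; on either version the ten-item total fails remotely.

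The effect on the summaries cannot be estimated, because the documents give neither a remote rate nor any expected SAS level. A reader might conclude that a real EPS signal would be hidden; that would require raters to score unexamined items as normal, which no section instructs. EPS summaries are descriptive (SAP 5.5), so no test, significance level or power figure is affected. This is a cheap improvement to safety data collection and summary.

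**What to change.** 1. Extend Protocol Table 6 footnote 11, with the matching lines in Protocol 8.2.2, SAP Table 1 and SAP 3.6.3. If Week 6 is remote, SAS may be done at an in-clinic Week 8 or 10 visit, as may AIMS and BARS if the visit is audio-only. State in SAP 5.5.7 that this rating is summarized as the mid-treatment value; SAP Table 2 is headed for efficacy assessments and should not be relied on for this.
2. Add an exception to SAP 3.6: SAS totals from any remote visit, and the observed items of AIMS and BARS from audio-only visits, are set to missing and not pooled. This requires the eCRF to record whether a remote visit was by video or audio.
3. Optionally, add change from Day 1 to the SAP 5.5.7 tables, as SAP 5.5.3, 5.5.5 and 5.5.6 do for laboratory values, vital signs and ECG. With missing ratings, the visit means come from different patients, and within-patient change avoids that.
4. Reconcile the SAS item list and scoring: 1 to 5 in Protocol 11.7.1 and SAP 4.6.1, 0 to 4 in Appendix G.

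The cost is one footnote with its matching lines, a short addition to the SAP, perhaps one table column, and the reconciliation. Some mid-treatment values will be two to four weeks late. There will be somewhat fewer Week 12 values, since no later treatment visit exists to which a remote Week 12 rating could move.

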8.2. Study Procedures

8.2.1 Screening Period Procedures (Week -5 and Week -3)

Prior to performing any study-related activities or evaluations, the patient must be thoroughly informed about all aspects of the study, including scheduled visits and activities. Patients will sign the study-specific consent form(s) prior to any screening procedure. Patients will be instructed to report all AEs that occur during the study from the time of informed consent forward.

Due to the COVID-19 pandemic and the possibility for site closures and/or travel restrictions, some Screening Period procedures (with the exception of PANSS) such as the MINI, medical history, review of concomitant medications) may be conducted remotely per Investigator discretion. The consent process must be conducted in the clinic and patients must sign the ICF in person in the clinic.

Patients should continue to take their prescribed AP medication throughout the Screening and Treatment Periods.

The following procedures will be performed at **Week -5**:

- Assessment of eligibility according to inclusion/exclusion criteria
- Conduct psychiatric evaluation and administer MINI International Neuropsychiatric Interview Psychotic Disorders, version 7.0.2 (MINI, Version 7.0.2; see [APPENDIX L](#))
- Demographics, medical history, including query for baseline signs/symptoms (ie, an AE with onset prior to dosing is to be recorded as a pretreatment AE)
- Review of concomitant medications including stable background AP therapy
- Full physical examination plus height and weight
- Vital signs including blood pressure, pulse rate, respiratory rate, and temperature
- Standard 12-lead ECG
- Urine pregnancy tests for women of childbearing potential
- Alcohol breath test
 - *A repeat alcohol breath test will be allowed within 48 hours of the first test. If the repeat test is positive, the patient must be excluded from the study*
- PANSS
- Assessment of suicidal ideation using C-SSRS (Baseline/Screening version)
- Serology, FSH, serum chemistry, hematology, and coagulation parameter evaluations
- Serum renal parameters and urinalysis

- Urine drug test
 - *Patients with a positive urine drug screen for benzodiazepines may be allowed in the study provided the drug was prescribed by a physician as an anxiolytic or sleep aid*
 - *Use of THC/cannabinoid products is allowed in the study*

The following procedures will be performed at **Week -3**:

- Continue to assess eligibility and review adverse events and concomitant medications including stable background AP therapy
- Urine drug test
 - *Patients with a positive urine drug screen for benzodiazepines may be allowed in the study provided the drug was prescribed by a physician as an anxiolytic or sleep aid*
 - *Use of THC/cannabinoid products is allowed in the study*
- Alcohol breath test
 - *Alcohol breath test must be negative for the patient to continue in the study*
- PANSS
- C-SSRS (Since Last Visit version)
- Blood sample for assessment of prescribed AP levels
 - *Sponsor or designee will provide confirmation of eligibility based on AP blood level*
- The Qualification period may be extended up to 2 weeks if repeat laboratory test results for confirmation of eligibility are pending

8.2.2 Treatment Period Procedures (Day 1 to Week 12)

The following procedures will be performed at **Day 1**:

- Continue to assess eligibility
- Following confirmation of eligibility, consenting patients will be randomized to 1 of the 4 Study Medication groups. The following procedures must be performed prior to administration of Study Medication:
 - Review of adverse events and concomitant medications including stable background AP therapy
 - Full physical examination plus and weight
 - Vital signs including blood pressure, pulse rate, respiratory rate, and temperature
 - Standard 12-lead ECG

- Urine pregnancy tests for women of childbearing potential
- Alcohol breath test
 - o *Alcohol breath test must be negative for the patient to be randomized to receive Study Medication*
- Serum chemistry, hematology, and coagulation parameter evaluations
- Serum renal parameters and urinalysis
- PANSS, PSP, CGI-S, SQLS
- C-SSRS (Since Last Visit version)
- SAS, AIMS, BARS
- Blood sample for genetic testing (if consent has been given)
- Administration of first dose of Study Medication in the clinic with food
- Dispensation of Study Medication to take home
 - *A 2-week supply of the Study Medication will be provided*

The following procedures will be performed at **Week 2 through Week 12:**

- Due to the COVID-19 pandemic and the possibility for site closures and/or travel restrictions, clinical laboratory blood draws may be performed by a Home Health Care service provider or by a local laboratory; other safety and efficacy assessments may be performed remotely via phone/audio or video conferencing platforms (with the exception of Facebook). Study personnel should strive to perform assessments within the visit window as shown in [Table 6](#) with the understanding that not all assessments may be able to be performed. Missed assessments will be recorded in the eCRF with notation that the missed assessment was due to the COVID-19 pandemic.
- The following procedures must be performed prior to administration of Study Medication:
 - Review of adverse events and concomitant medications including stable background AP therapy
 - Brief physical examination plus weight; vital signs including blood pressure, pulse rate, respiratory rate, and temperature (Weeks 2, 4, 6, 8, 10)
 - Full physical examination plus weight
 - Vital signs including blood pressure, pulse rate, respiratory rate, and temperature (Week 12)

- Standard 12-lead ECG (Weeks 6 and 12 only; if Week 6 visit is a remote visit, ECG assessment may be performed at Week 8 or 10)
- Urine pregnancy tests for women of childbearing potential
- Alcohol breath test
 - o *Patient may be discontinued if they test positive at any two visits during the treatment period*
- Serum chemistry, hematology, and coagulation parameter evaluations (Weeks 6 and 12 only)
- Serum renal parameters and urinalysis
- Blood sample for assessment of CTP-692 levels (pre-dose if dose of Study Medication is administered in the clinic at Weeks 2, 4, 6, 8, and 10)
 - o *If possible, time of last dose taken should also be recorded*
- Dispensation of Study Medication to take home
 - *A 2-week supply of the Study Medication will be provided at each visit except Week 12*
 - *When study assessments are not conducted in the clinic due to the COVID-19 pandemic, the Study Medication may be sent directly to the patient*
- PANSS (Weeks 2, 4, 8, 10, and 12)
- CGI-S (Weeks 2, 4, 6, 8, 10, and 12)
- C-SSRS (Since Last Visit version)
- PSP (Weeks 6 and Week 12 only)
- SQLS (Week 12 only)
- SAS, AIMS and BARS (Weeks 6 and Week 12 only)
- Blood sample for assessment of CTP-692 levels (post-dose; Week 12 only)
 - *Blood sample should be taken at the end of the visit*
 - *Time of CTP-692 dose and blood draw should be recorded*
- Administration of dose of Study Medication in the clinic with food *at the Week 12 visit*
 - Post Dose blood sample for assessment of CTP-692 levels (Week 12 only)
 - o *Blood sample should be taken at the end of the visit*
 - o *Time of CTP-692 dose and blood draw should be recorded*

